## 5. ETHICAL ASPECTS

The study will be submitted by the investigator(s) or the Sponsor (or its legal representative) in accordance with local regulations to and approved by an appropriate Independent Ethical Review Committee / Institutional Review Board and a Regulatory Authority if required by the national laws of the countries where the study will be conducted.

The investigators and the Sponsor will ensure that the study is conducted in full conformance with the principles of the “Declaration of Helsinki” 1964, as revised from time to time or with the laws and regulations of the country in which the research is conducted, whichever affords the greater protection to the individual. For the study, the principal investigators will ensure compliance with the latest European Union (EU) Data Protection Directive or with local law especially if it affords greater protection to the patient.

If required according to the national regulations and laws, it is the responsibility of the Investigator or a person designed by the Investigator (if acceptable by local regulations) to obtain written informed consent from each potential subject prior any study data collection being carried out. However, when allowed by the national regulations and laws, the investigators of the present study will apply to the Independent Ethical Review Committee / Institutional Review Board for a waiver of the need to obtain informed consent. The reasons are:

- (i) it is a retrospective study that involves no interventions with human subjects. Medical records will be reviewed, but none of the patients will be contacted;
- (ii) the research involves no more than minimal risk to the subjects;
- (iii) the waiver will not adversely affect the rights and welfare of the subjects; moreover, the research could not practicably be carried out without the waiver;
- (iv) the information collected does not include information that may be damaging to the individual should it be wrongfully disclosed; patients’ privacy will be protected throughout the study;
- (v) data will be anonymized and stored electronically in a restricted access network folder and will only be accessible to the research team.

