#### 3.1. Eligibility criteria

The eligibility criteria are intentionally broad for trying to exclude as few patients as possible so that true population-based data can be obtained. To be eligible for the present study, patients should fulfill the following inclusion and exclusion criteria.

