##### Inclusion criteria:

- Diagnosis of invasive breast cancer between January 2000 and December 2020;
- Breast cancer diagnosis at the age of  $\leq 40$  years;
- Known presence of germline *BRCA* pathogenic variant.

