### 3.3. Data collection

For all consecutive eligible patients included in the study from each participating Institution, their medical records will be retrieved and anonymized data entered into a database. The following information will be collected, if available:

- 1) Baseline characteristics: body mass index; smoking habit; age at menarche; age at menopause; menopausal status at the time of breast cancer diagnosis; use of birth control pills; prior children before breast cancer diagnosis; history of spontaneous abortion; history of induced abortion; prior treatment for infertility; prior gynecological surgery and/or medical history with possible impact on fertility.
- 2) Breast cancer history: date of diagnosis; age at diagnosis; disease stage; laterality of the primary tumor; type of breast and axillary surgery; use of breast reconstruction surgery; grade; histology; tumor size and nodal status (for patients who underwent primary systemic therapy, only clinical tumor size and nodal status will be collected); hormone receptor status (estrogen and progesterone receptors); HER2 status.
- 3) Treatment of the primary tumor: timing of systemic therapy administration; use of chemotherapy (type and number of cycles); use of endocrine therapy (type and duration); use of anti-HER2 targeted therapy (type and duration); use of radiotherapy.
- 4) Survival status: any recurrence of invasive breast cancer including date of the event; any second primary breast cancer including date of the event; any second primary malignancy including date of the event; date of last follow-up and/or death; cause of death (breast cancer-related or not).
- 5) Ovarian function after chemotherapy: treatment-induced POF; age at menopause.

6) Pregnancy after breast cancer: any pregnancy including date of the event; pregnancy outcome; gestational age at delivery; any pregnancy/fetal/birth complications; breastfeeding and its duration; use and type of ART.

7) BRCA mutation: date of *BRCA* testing; type of *BRCA* mutation; use and date of breast prophylactic surgery; use and date of gynecological prophylactic surgery.

8) Additional information: diagnosis of breast cancer during pregnancy, availability of digital scanned images for TILs analysis

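### Where consent is required from every woman, a site may be able to enter survivors only, and the plan pools such sites with waiver sites without recording the consent route.

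*Combined protocol and SAP*

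**What the plan says.** Section 5 foresees two routes into the study. Where national law demands it, the investigator is responsible "to obtain written informed consent from each potential subject prior any study data collection being carried out". Where national law permits, the investigators "will apply to the Independent Ethical Review Committee / Institutional Review Board for a waiver of the need to obtain informed consent", and one reason given is that "the research could not practicably be carried out without the waiver". Neither route mentions women who have died or been lost to follow-up.

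The sampling is meant to be complete. Section 3.3 opens with "For all consecutive eligible patients included in the study from each participating Institution", and Section 3.1 sets broad criteria in order to "exclude as few patients as possible so that true population-based data can be obtained". Eligibility is "Diagnosis of invasive breast cancer between January 2000 and December 2020", and the current protocol version is dated January 2022.

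Section 4 puts all included patients into the extended Cox model, draws cases and controls for the matched analysis from the same pool, and estimates the pregnancy rate by Kaplan-Meier. It does not stratify by centre or consent route, does not use delayed entry at consent, and has no analysis limited to waiver sites. The data items in Section 3.3 include neither consent route nor consent date.

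**The concern.** With diagnoses reaching back to 2000, many eligible women will have died before their site collects data. A woman who has died cannot sign. If her country's law makes no exception for her, a site that follows Section 5 leaves her out, and what it sends is a set of survivors. A waiver site sends everyone.

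Death is the whole of OS, breast cancer death is the whole of BCSS, and death also counts in DFS. A consent-only site therefore contributes follow-up with no deaths before consent, and only those relapses that the woman survived. Pooling makes absolute survival look too good. It can also distort the comparison by pregnancy: if pregnant women are over- or under-represented at the sites with artificially good survival, pregnancy takes on part of that difference.

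The two methods in Section 4 against guaranteed-time bias deal with survival from diagnosis to pregnancy. They do not address survival from diagnosis to consent.

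**Working it through.** The plan gives no figure for this selection. Its power statement plays no part here, except that its target hazard ratios of 0.75 and 0.80 serve as a yardstick.

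**Input from the plan.** 5-year DFS of 65% in the non-pregnant cohort (Section 4). Under an exponential model the hazard is −ln(0.65)/5 = 0.0862 per year.

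**Assumptions, not in the documents.**
- Diagnoses spread evenly over 2000–2020, with data collected in 2022.
- Death after a DFS event at 0.15 per year, with 0.30 as an alternative.
- Every living woman is reachable and consents.
- 15% of women have a potential pregnancy time 1 to 7 years after diagnosis, counted only if it comes before relapse. About 9% are then observed to become pregnant, close to the plan's 10%.
- At consent-only sites, women who died before data collection are removed.

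**Step 1: who is left.** In simulation (at least one million women per scenario) 64.4% of eligible women are alive at data collection. If 30% of eligible women belong to consent-only sites, those sites supply 0.30 × 0.644 / (0.70 + 0.30 × 0.644) = 0.193/0.893 = 22% of the women actually included.

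**Step 2: absolute survival.** At a consent-only site, simulated 5-year DFS is 0.82 and OS is 1.00 by construction. A hand check of pooled DFS at 30% gives 0.784 × 0.65 + 0.216 × 0.82 = 0.687. The pooled Kaplan-Meier estimates at 0.15 per year are:

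| Eligible women at consent-only sites | 5-year DFS | 10-year OS |
|---|---|---|
| 0% | 65% | 69% |
| 10% | 66% | 71% |
| 30% | 68.6% | 75% |
| 50% | 71.5% | 80% |

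With 0.30 per year after relapse, a 25% share moves 5-year DFS to 68.5% and 10-year OS from 57% to 63%.

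**Step 3: pregnancy rate.** With equal pregnant shares and no effect of pregnancy, the 10-year Kaplan-Meier rate goes from 11.7% to 11.9% at a 25% share and to about 12.3% at 50%. This is a small change.

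**Step 4: DFS hazard ratio, equal pregnant shares.** With pregnancy as a time-varying exposure and a true ratio of 1, the estimate stays at about 1.00 for shares up to 50%. With a true ratio of 0.75 it is 0.74–0.75 at a 25% share and 0.73–0.74 at 50%.

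**Step 5: unequal pregnant shares, no true effect on DFS.** OS is shown as a factor. In this model the OS ratio is already about 0.68 with no consent sites, because only relapse-free women become pregnant.

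| Consent-only share | Pregnant share at consent sites | DFS ratio | Factor on OS ratio |
|---|---|---|---|
| 30% | doubled | about 0.92 | about 0.80 |
| 30% | halved | about 1.06 | about 1.13 |
| 10% | doubled | about 0.96 | about 0.93 |
| 10% | halved | about 1.02 | about 1.05 |

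**Step 6: effect of stratifying.** Stratifying by consent basis returns the DFS ratio to about 1.00 in each of these scenarios, and the OS ratio to its value without consent selection. It keeps every patient.

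**The case against.** The consent duty is conditional. Where a country's law does not require consent for a deceased woman, or where earlier research consent suffices, Section 5 imposes no restriction. The waiver is already to be sought wherever it is allowed. The documents do not say how many sites, if any, need consent from every subject, and extraction in 2022 for all sites is an assumption, since version 1.0 dates from December 2016. All of this stands. It makes the size conditional, but it does not remove the gap: the protocol admits both routes, and its data list could not show afterwards which applied.

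It is also true that the primary comparison barely moves when pregnant shares are equal. The shifts in Step 5 need a twofold difference in pregnant share, for which the documents give no evidence in either direction.

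Two stronger readings are tempting.
- A reader might infer that the statement "Medical records will be reviewed, but none of the patients will be contacted" is false at consent sites. It is listed as a reason for a waiver application, so it describes waiver sites. A site that must seek consent does not rely on it.
- A reader might infer that consent sites should be left out of the main analyses. They contribute no deaths before consent, but they do contribute DFS events: about 14% of all DFS events in the 30% scenario. Exclusion would discard these, whereas stratification removes the distortion between sites without that loss.

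**Conclusion.** The point holds in conditional form. As written, the plan can mix survivor-only sites with full-cohort sites, contrary to its aim of consecutive, population-based inclusion, and it collects nothing that would reveal or correct this.

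Absolute DFS and OS are the most exposed: roughly 1 to 4 percentage points for 5-year DFS, and 2 to 6 for 10-year OS, when 10% to 30% of eligible women are at consent-only sites. The pregnancy rate changes little. The DFS hazard ratio is essentially unaffected with equal pregnant shares. With a twofold imbalance in the 30% case, a null DFS ratio becomes about 0.92 or 1.06 and the OS ratio shifts by a factor of about 0.80 or 1.13. Those shifts are not negligible beside targets of 0.75 and 0.80.

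All of these sizes rest on the assumed share of consent-only sites, the assumed mortality after relapse, and the 2022 extraction date. The documents do not support a claim that the study's results are biased by any particular amount.

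**What to change.** 1. **Section 3.3:** add one field for consent basis with three values: waiver for all women; waiver for deceased or unreachable women; consent from every subject.
2. **Section 4, main analyses:** stratify the Cox models by consent basis and match within it in the matched analysis. Consent basis should not be among the matching criteria that are relaxed when a third control is missing.
3. **Section 4, sensitivity analysis:** pre-specify that absolute DFS, BCSS, OS and the pregnancy rate are also reported for sites able to include deceased and lost women. Stratifying does not undo survivor selection within consent-only sites. When all women are at such sites, the simulation gives a DFS ratio of 0.71–0.72 for a true 0.75.
4. **Section 5:** state that the waiver request covers deceased and unreachable women where the law allows.

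Consent sites stay in the main analyses. The cost is one extra column, a little more analysis, short amendments to the three sections, and somewhat fewer possible matches. If few sites need consent from every subject, almost nothing changes.

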## 6. DATA HANDLING AND RECORD KEEPING

The Patient's right to confidentiality is paramount. Collected data will be anonymized. All data will be kept confidential and will be used only for the purpose of this study. Local data privacy laws, rules and guidelines must be respected.

## 7. DATA CONFIDENTIALITY AND TIMELINE

Data will be provided by investigators of the participating Institutions in confidence to Institut Jules Bordet, where they will be kept secure. The data collection will be performed by [name] and [name], whereas the database set up, data cleaning and the statistical analysis will be performed by the study secretariat and statisticians in charge of the overall analysis once the database has been cleaned and locked.

The proposed timeline for project from the receipt of all data, database assembly and cleaning, statistical analysis to first results is 6 months.

## 8. PUBLICATION POLICY

A manuscript summarizing the results of the main analysis will be prepared for submission to and publication in a peer-reviewed scientific journal. Regular emails, teleconferences and/or face-to-face meetings will be organized to discuss progress of the data analysis. The manuscript will be prepared by one or more of the study chairs along with the study secretariat and statistical team and will be submitted to the all collaborators for review. Authorship will be based on number of included patients: the 3 Institutions with the highest number of included patients will be granted to up to two authors, while each of the collaborating Institutions will allocate one or no author.

Any other publication arising from this project will be made on behalf of the study chairs directly involved in that specific analysis and the principal investigators from the participating Institutions that actively contributed to that specific analysis.

All authors will be given sufficient time to provide comments and attempts will be made to come to mutual agreement. No financial benefits will be pursued or derived by the study and the corresponding results.

## 9. FUNDING

This project will be supported by Institut Jules Bordet. Unfortunately, it cannot be offered any financial reimbursement for involved investigators.

